##### Phase 1b Dose Escalation

- Incidence of dose-limiting toxicity (DLT) as defined in Section 3.2.

The secondary endpoints are as follows:

##### Phase 1b Dose Escalation

- PK parameters ( $T_{last}$ ,  $T_{max}$ ,  $C_{max}$ ,  $C_{trough}$ ,  $AUC_{last}$ ,  $AUC_{tau}$  and  $t_{1/2}$ , as applicable) for GS-4224 in subjects with advanced solid tumors.

##### Phase 2 Dose Expansion

- Incidence of Grade  $\geq 3$  treatment-emergent adverse events (TEAEs) in Cohort B1 subjects with advanced solid tumors
- Incidence of Grade  $\geq 3$  treatment-emergent laboratory abnormalities in Cohort B1 subjects with advanced solid tumors

CCI [REDACTED]

■ [REDACTED]

CCI [REDACTED]

■ [REDACTED]

■ [REDACTED]

■ [REDACTED]

■ [REDACTED]

■ [REDACTED]

[figure not shown]
### 3.2. Study Design

This is an open-label, multicenter, sequential dose escalation and dose expansion study to evaluate the safety, tolerability, PK, and efficacy of GS-4224 in subjects with advanced solid tumors. The study will consist of 2 parts: the dose escalation portion (Phase 1b), followed by dose expansion (Phase 2) in subjects with tumors for which PD-1/PD-L1 treatments are approved or are known to be active.

#### 3.2.1. Dose Escalation (Phase 1b)

The overall Phase 1b study design is presented graphically in [Figure 3-1](#).

**Figure 3-1. Phase 1b Study Design Schema**

DL dose level; HV healthy volunteers; QD once a day; BID twice a day; RP2D recommended Phase 2 dose

Subjects with advanced solid tumors who have failed or are intolerant to standard therapy or for whom no standard therapy exists will be sequentially enrolled at progressively higher dose levels to receive oral GS-4224 as monotherapy once daily (400 1500 mg QD cohorts) and as monotherapy at 1000 mg twice daily (1000 mg BID cohort).

Dose escalation will proceed using a standard 3+3 design. The starting dose is 400 mg QD, with subsequent doses of 700 mg QD, 1000 mg QD, 1500 mg QD, and 1000 mg BID. Dose level increases will be 3-fold or less.

**Table 3-1. Dose Escalation (Phase 1b) Dose Levels**

Dose Level Schema	
GS-4224 (mg)	Fold Increase
400 QD	-
700 QD	≤ 3×
1000 QD	≤ 3×
1500 QD	≤ 3×
1000 BID	≤ 3×

In the 1000 mg BID dose cohort, at least 6 (as part of the initial 3+3 design) and up to an additional 14 subjects (for a total of 20 subjects) with locally advanced, inoperable or metastatic cancer expressing PD-L1 (tumor proportion score [TPS] ≥ 10% or combined positive score [CPS] ≥ 10) and who have not previously been treated with anti-PD-1/L1 antibodies will be enrolled. The additional 14 subjects will not be enrolled at the 1000 mg BID dose level if the subject incidence of DLTs is > 1 in the first 6 subjects. If the subject incidence of DLTs is > 1 in the first 6 subjects at 1000 mg BID, then 20 additional subjects with locally advanced, inoperable or metastatic cancer expressing PD-L1 [TPS ≥ 10% or CPS ≥ 10] and who have not previously been treated with anti-PD-1/L1 antibodies will enroll at the MTD. Tumor types of interest include non-small cell lung cancer (NSCLC), melanoma, renal cell carcinoma (RCC), urothelial, esophageal, hepatocellular carcinoma (HCC), cutaneous squamous cell, Merkel cell, MSI-H cancers, and cHL. See [Appendix 3](#) for the PD-L1 expression requirement for specific tumor types.

For the 1000 mg BID dose cohort, subjects must have available sufficient and adequate formalin-fixed tumor tissue sample preferably from a biopsy of a tumor lesion obtained either at the time of or after the diagnosis of advanced disease has been made and from a site not previously irradiated. Alternatively, subjects must agree to have a biopsy taken prior to entering the study to provide adequate tissue. Subjects with melanoma, Merkel cell, MSI-H cancers, and cHL are not required to have archival or fresh biopsy tissue.

The safety and tolerability of each dose level will be assessed by a safety review team (SRT) after up to 6 subjects enrolled in the dose level have been followed for at least 21 days after the first dose of GS-4224 or 2 DLTs have been observed, whichever is earlier. See Section 3.2.3 for more information about the SRT.

The initial block of each dose consists of 3 subjects. Dose escalation may occur if no subjects experience DLTs during the first 21 days of study drug dosing. If 1 subject within the initial cohort of 3 subjects experiences a DLT during the first 21 days of study drug dosing, an additional 3 subjects will be enrolled at the same dose level. If no DLTs are observed in the additional 3 subjects, dose escalation will occur. If 2 or more of the 6 subjects experience DLTs within the first 21 days, dose de-escalation to an intermediate dose will occur. The MTD is the

highest dose level with a subject incidence of DLTs during the first 21 days of study drug dosing of 0 or 1 out of 6. A minimum of 6 subjects need to be treated at a dose level before this dose level can be deemed as the MTD. A subject who is withdrawn from the study before the completion of the first 21 days for a reason other than a DLT will be replaced.

If 2 or more delayed DLT-type AEs are noted after the first 21-day observation period within a dose escalation cohort, further accrual at all sites will be held pending safety analysis of the event, and will be restarted only with investigator and sponsor approval.

The SRT will review safety and relevant clinical data and make the dose escalation/stay/de-escalation decision. Source Data Verification (SDV) is not required to be performed prior to SRT meetings, as there will be alternative quality control checks implemented. These checks will be described in the SRT Charter.

#### 3.2.1.1. DLT Definition

A DLT is any toxicity defined below excluding toxicities clearly related to disease progression or disease-related processes occurring during the DLT assessment window (Day 1 through Day 21):

- Grade  $\geq$  4 neutropenia (absolute neutrophil count [ANC]  $<$  500/mm^3)
- Grade  $\geq$  3 neutropenia (ANC  $<$  1000/mm^3) with fever (a single temperature of  $>$  38.3°C or a sustained temperature of  $\geq$  38°C for more than 1 hour)
- Grade  $\geq$  3 thrombocytopenia
- Grade  $\geq$  2 bleeding (eg, GI, respiratory, epistaxis, or purpura)
- Grade  $\geq$  3 anemia
- Grade  $\geq$  3 or higher non-hematologic toxicity, except:
  - Grade 3 nausea or emesis with maximum duration of 48 hours on adequate medical therapy
  - Grade 3 diarrhea which persists for  $<$  72 hours in the absence of maximal medical therapy.
- Grade  $\geq$  2 non-hematologic TEAE that in the opinion of the investigator is of potential clinical significance such that further dose escalation would expose subjects to unacceptable risk
- Continuous treatment interruption of  $\geq$  7 days due to unresolved toxicity
- Any toxicity event that precludes further administration of GS-4224

- Any Grade 3 or Grade 4 elevation in aspartate aminotransferase (AST) or alanine aminotransferase (ALT) associated with a Grade 2 elevation in bilirubin lasting  $\geq 7$  days
- An irAE for which immunotherapy should be permanently discontinued (eg, any grade encephalitis, Grade 3 myocarditis, reoccurrence of the same Grade 3 adverse reaction).

For certain toxicities, such as laboratory assessments without a clear clinical correlate, a discussion between the investigator and medical monitor may take place to determine if this AE should be assessed as a DLT.

Excluded from this definition:

- Grade 3 AEs of tumor flare (defined as local pain, irritation, or rash localized at sites of known or suspected tumor)
- Grade 3 rash without systemic signs or symptoms
- Grade 3 irAE that resolves to a Grade 1 or less within 21 days, except as described above.

#### 3.2.1.2. Recommended Phase 2 Dose Determination

The RP2D will be determined by Gilead in discussion with the SRT based on all relevant clinical data from all subjects treated in the escalation phase. The RP2D will not exceed the MTD and will consider toxicities through 90 days of dosing.

CCI

### **3.2.2. Dose Expansion (Phase 2)**

Dose expansion may begin when the RP2D has been determined.

The dose expansion phase includes the following cohort:

*Cohort B1 (Basket Cohort expressing PD-L1 [TPS  $\geq$  1% or CPS  $\geq$  1 or  $\geq$  10] or MSI-H cancers, single arm, open-label study of GS-4224)*

To further characterize the safety and preliminary efficacy of GS-4224, a cohort of ~40 subjects with locally advanced, inoperable or metastatic cancer expressing PD-L1 [TPS  $\geq$  1% or CPS  $\geq$  1] will be enrolled at the RP2D level. Tumor types of interest include NSCLC, melanoma, RCC, urothelial, gastric, squamous cell head and neck, HCC, MSI-H cancers, Merkel cell, cutaneous squamous cell, esophageal cancers, and cHL. See [Appendix 3](#) for the PD-L1 expression requirement for specific tumor types.

### **3.2.3. Safety Review Team**

An SRT will be established to assess safety, make decisions on dose escalation, define the MTD, and propose RP2D for dose expansion consideration.

The SRT will consist of at least 1 investigator and the following Gilead study team members: the medical monitor, representatives from Global Patient Safety (GLPS) (formerly Gilead Pharmacovigilance and Epidemiology), Clinical Operations, and Biostatistics. Others may be invited to participate as members of the SRT if additional expertise is desired. The medical monitor serves as the chair of the SRT.

An SRT Charter (or similar document) will be agreed by all SRT members prior to the first SRT meeting. The SRT Charter will describe the dose escalation process, including the following:

- Data required for review before initiating the next specified dose
- Data quality required
- Stopping rules for individual and for the study
- Minimum quorum of study and sponsor personnel required to make decisions
- Who makes the final dose escalation decision and documentation of the decision

### **3.3. Study Treatments**

The study drug is GS-4224. Subjects will be given GS-4224 tablets once daily in the 400-1500 mg QD cohorts and twice daily in the 1000 mg BID cohort.

Formulation, packaging, and dosing regimens are further described in [Section 5](#).

### 3.4. Duration of Treatment

GS-4224 will be administered until disease progression, unacceptable toxicity, substantial noncompliance with study procedures or study drug, study discontinuation or withdrawal from study.

### 3.5. Study Discontinuation Criteria

The entire study may be discontinued in the event of any of the following:

- New information leading to unfavorable risk-benefit judgment of GS-4224
- Sponsor's decision
- Poor enrollment of subjects, making completion of the study within an acceptable timeframe unlikely
- Discontinuation of development of GS-4224

Health authorities and independent ethics committees (IECs)/institutional review boards (IRBs) will be informed about study discontinuation in accordance with applicable regulations.

The entire study may be terminated or suspended upon request of health authorities.

Recruitment at a center may be stopped for reason that may include low recruitment, protocol violation, or inadequate data recording quality control and quality assurance.

### 3.6. Poststudy Care

Upon withdrawal from study treatment, subjects may receive the care upon which they and their physicians agree.

### 3.7. Source Data

The subject identification numbers captured by the interactive voice/web response system (IXRS) are considered source data.

CCI

[REDACTED]

CCI

[REDACTED]

CCI [REDACTED]

[REDACTED]

[REDACTED]

[REDACTED]

**CCI**

[REDACTED]

[REDACTED]

[REDACTED]

[REDACTED]

[REDACTED]

[REDACTED]

**CCI**

[REDACTED]

[REDACTED]

## 4. SUBJECT POPULATION

### 4.1. Number of Subjects and Subject Selection

Up to 120 subjects will be enrolled at approximately 35 centers in the US, Europe, and rest of world (ROW).

Phase 1b (Dose Escalation): Up to 44 subjects

CCI

Phase 2 (Dose Expansion):

- Cohort B1 (Basket): Approximately 40 subjects

#### 4.1.1. Target Population

Phase 1b: Adult subjects with a histologically or cytologically confirmed advanced malignant solid tumor that is refractory to or intolerant of standard therapy or for which no standard therapy is available. For the 1000 mg BID cohort, histologically or cytologically confirmed advanced tumor expressing PD-L1 (TPS  $\geq$  10% or CPS  $\geq$  10) or MSI-H cancers. Tumor types of interest include NSCLC, melanoma, RCC, urothelial, esophageal, HCC, cutaneous squamous cell, Merkel cell, MSI-H cancers, and cHL. PD-L1 expression will not be required for Merkel cell, melanoma, MSI-H cancers, and cHL. See [Appendix 3](#) for the PD-L1 expression requirement for specific tumor types.

Phase 2 (See [Appendix 3](#)):

- Cohort B1 (Basket): Histologically or cytologically confirmed advanced tumor expressing PD-L1 (TPS  $\geq$  1% or CPS  $\geq$  1 or  $\geq$  10) or MSI-H cancers. Tumor types of interest include NSCLC, melanoma, RCC, urothelial, gastric, squamous cell head and neck, HCC, MSI-H cancers, Merkel cell, cutaneous squamous cell, esophageal cancers, and cHL. See [Appendix 3](#) for the PD-L1 expression requirement for specific tumor types.

#### 4.1.2. Subject Replacement

A subject who is withdrawn from the study before the completion of the first 21 days for a reason other than a DLT or who receives less than 16 of 21 doses of GS-4224 in the first 21 days will be replaced.

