### **5.3. Dosage and Administration of GS-4224**

The GS-4224 study drug will be supplied as tablets in strengths of 100 mg, 200 mg, and/or 500 mg. GS-4224 will be taken once daily in the morning (400 1500 mg QD cohorts) and 1000 mg twice daily separated by approximately 12 hours (1000 mg BID cohort).

On days with intensive PK (Cycle 1 Days 1 and 15), study drug will be administered at the same time every morning with approximately 240 mL of water and following an overnight fast (no food or drinks, except water, for at least 8 hours). For study treatments including those of more than 5 tablets, up to an additional 120 mL of water can be administered, if necessary. Water will be withheld starting 1 hour before and for 2 hours after dose administration, except for water given with the study drug. Water may be consumed by subjects following the 2-hour blood draw for the remainder of the collection period. A meal (standardized lunch) will be provided to subjects after the 4 hour postdose blood draw. All other fluids will be allowed after the 4 hour postdose blood draw.

For all days that study drug is administered where no intensive PK assessments are required, GS-4224 should be administered without regard to food at approximately the same time every morning. Subjects should administer study drug with a full glass of water.

If vomiting occurs after administration of study drug, the dose should not be repeated.

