#### 5.4.2. Treatment Interruption for GS-4224

The following qualifying AEs must lead to interruption of GS-4224 administration, unless there is another obvious attribution (eg, trauma, PD):

- Dose interruption should occur for Grade  $\geq 3$  serum creatinine (more than  $3\times$  baseline) toxicity;
- Dose interruption should occur in subjects with any Grade 3 or Grade 4 elevation in AST or ALT associated with a Grade 2 elevation in bilirubin;
- Any Grade  $\geq 3$  non-skin, drug-related AE with the following exceptions:

Do not interrupt treatment for Grade  $\geq 3$  fatigue

- Any Grade  $\geq 3$  drug-related laboratory abnormality with the following exceptions for lymphopenia:

Grade 3 lymphopenia does not require a dose interruption

- Any AE, laboratory abnormality, or intercurrent illness which, in the judgment of the investigator, warrants interrupting the dose of study drug

Subjects receiving GS-4224 who have drug-related toxicities that meet the criteria for dose interruption should have GS-4224 interrupted until criteria to resume treatment are met.

**Note:** GS-4224 should be discontinued in subjects who experience any Grade  $\geq 3$  skin drug-related AE with systemic signs or symptoms or suspected Stevens-Johnson syndrome (SJS) or toxic epidermal necrolysis (TEN).

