### 6.9. Assessments for Premature Discontinuation from Study

If a subject discontinues study dosing (eg, as a result of an AE), every attempt should be made to keep the subject in the study and continue to perform the required study-related follow up and procedures (see Section 6.10, Criteria for Discontinuation of Study Treatment). If this is not possible or acceptable to the subject or investigator, the subject may be withdrawn from the study.

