#### 8.3.1.4. DLT-Evaluable Analysis Set

The DLT-Evaluable Analysis Set includes all subjects in the Safety Analysis Set who enroll to the dose escalation cohorts (up to the first 6 subjects in the 1000 mg BID dose escalation cohort; CCI [REDACTED]), complete  $\geq 75\%$  of the prescribed study treatment and have safety assessments through the protocol-specified DLT assessment window (first 21 days of study dosing, inclusive) or have experienced a DLT prior to the completion of first 21 days of study dosing. Safety assessment relevant to the DLT-Evaluable Analysis Set definition will include laboratory serum chemistry tests and hematology tests as specified in the protocol. Determination of the MTD will be based on the DLT-Evaluable Analysis Set.

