1.2.1. Dose Escalation (Phase 1b)

Subjects with advanced solid tumors who have failed or are intolerant to standard therapy or for whom no standard therapy exists will be sequentially enrolled at progressively higher dose levels of oral GS-4224 as monotherapy.

Dose escalation will proceed using a standard 3+3 design. The starting dose is 400 mg once daily (QD), with subsequent doses of 700 mg QD, 1000 mg QD, 1500 mg QD, and 1000 mg twice daily (BID). Dose level increases are 3-fold or less.

Dose Level Schema	
GS-4224 (mg)	Fold Increase
400 QD	-
700 QD	$\leq 3\times$
1000 QD	$\leq 3\times$
1500 QD	$\leq 3\times$
1000 BID	$\leq 3\times$

In the 1000 mg BID dose cohort, at least 6 (as part of the initial 3+3 design) and up to an additional 14 subjects (for a total of 20 subjects) with locally advanced, inoperable or metastatic cancer expressing PD-L1 (tumor proportion score [TPS] $\geq 10\%$ or combined positive score [CPS] ≥ 10) and who have not previously been treated with anti-PD-1/L1 antibodies will be enrolled. The additional 14 subjects will not be enrolled at the 1000 mg BID dose level if the subject incidence of DLTs is > 1 in the first 6 subjects. If the subject incidence of DLTs is > 1 in the first 6 subjects at 1000 mg BID, then 20 additional subjects with locally advanced, inoperable or metastatic cancer expressing PD-L1 [TPS $\geq 10\%$ or CPS ≥ 10] and who have not previously been treated with anti-PD-1/L1 antibodies will enroll at the MTD.

The initial block of each dose consists of 3 subjects. Dose escalation may occur if no subjects experience DLTs during the first 21 days of study drug dosing. If 1 subject within the initial cohort of 3 subjects experiences a DLT during the first 21 days of study drug dosing, an additional 3 subjects will be enrolled at the same dose level. If no DLTs are observed in the additional 3 subjects, dose escalation will occur. If 2 or more of the 6 subjects experience DLTs within the first 21 days, dose de-escalation to an intermediate dose will occur. The MTD is the highest dose level with a subject incidence of DLTs during the first 21 days of study drug dosing of 0 or 1 out of 6. A minimum of 6 subjects need to be treated at a dose level before this dose level can be deemed as the MTD. A subject who is withdrawn from the study before the completion of the first 21 days for a reason other than a DLT will be replaced.

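### The dose-count limb of the replacement rule (Protocol 4.1.2) has no DLT exemption and fits only once-daily dosing, so it does not agree with the DLT-Evaluable definition

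*Protocol*

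**What the plan says.** **Replacement.** Protocol 4.1.2 has two limbs. The first covers withdrawal from the study within 21 days and exempts withdrawal because of a DLT. The second covers a subject "who receives less than 16 of 21 doses of GS-4224 in the first 21 days will be replaced", and the exemption is not attached to it. Protocol 3.2.1 has only the withdrawal limb: a subject withdrawn in that period "for a reason other than a DLT will be replaced". The synopsis says the same, and so does SAP 1.2.1: "before the completion of the first 21 days for a reason other than a DLT will be replaced". None of these three mentions a dose count.

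**Evaluability.** Protocol 8.3.1.4 admits a subject who completes at least 75% of prescribed treatment with safety assessments through the window, "or have experienced a DLT prior to the completion of first 21 days of study dosing". The second route has no dose condition. SAP 3.1.4 repeats both routes and glosses the 75% as 16 of 21 doses, for all cohorts alike. Both sections base the MTD on this set.

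**Dosing and toxicity.** Protocol 5.3 gives the top cohort "1000 mg twice daily separated by approximately 12 hours (1000 mg BID cohort"). Under Protocol 3.2.1.1, a continuous interruption of at least "7 days due to unresolved toxicity" is a DLT. Protocol 5.4.2 requires a hold for any Grade 3 or higher "drug-related laboratory abnormality with the following exceptions for lymphopenia". Protocol 6.9 says that when dosing stops "every attempt should be made to keep the subject in the study".

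**The concern.** DLT incidence is the only primary endpoint, the DLT table (SAP 7.1.7) is built on the DLT-Evaluable set, and the MTD is read from the same set. With three or six subjects at a level, each classification matters.

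Three things do not fit together:

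- The dose limb of 4.1.2 catches subjects whose low dose count is a consequence of a DLT, although the analysis set keeps them.
- The count of 16 is tied to a once-daily schedule, although one cohort takes two doses a day.
- Some subjects who miss doses because of toxicity, without meeting a DLT criterion, fall out of the denominator. That selects the denominator partly on tolerability.

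**Working it through.** **1. The plan's own figure.** Inputs: a 21-day window, one dose a day, and the 75% threshold. 0.75 × 21 = 15.75, so 16 doses are needed, and 16/21 = 76.2%. The SAP gloss reproduces for once-daily dosing.

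**2. A once-daily subject with a DLT.** A 7-day toxicity hold completed inside the window is a DLT under 3.2.1.1. It leaves at most 21 − 7 = 14 doses, and 14/21 = 66.7%.

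- Under 4.1.2, 14 is below 16 and the subject is replaced.
- Under 8.3.1.4 and SAP 3.1.4, the subject is evaluable through the DLT route.
- Under 3.2.1 and SAP 1.2.1, a subject who stays on study is not replaced at all.

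Counting this subject and adding a replacement gives 3 + 1 = 4 or 6 + 1 = 7 evaluable subjects. Section 3.2.1 gives decision rules for 3 and 6 only. The same happens with any DLT that stops dosing before dose 16 while the subject remains on study.

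**3. The BID cohort.** Prescribed doses: 2 × 21 = 42. Threshold: 0.75 × 42 = 31.5, so 32 doses are needed.

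| BID doses taken | Share of 42 | Literal count of 16 | 75% rule |
|---|---|---|---|
| 16 | 38.1% | met | not met |
| 31 | 73.8% | met | not met |
| 32 | 76.2% | met | met |

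A DLT-free subject anywhere from 16 to 31 doses is not replaced on a literal count, yet is not evaluable under Protocol 8.3.1.4. One such subject among six leaves 6 − 1 = 5 evaluable. Read as a proportion, 16/21 equals 32/42 exactly and the conflict disappears.

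**4. Toxicity shortfalls below a DLT.** Afebrile Grade 3 neutropenia judged drug-related requires a hold (5.4.2) but is not a listed DLT (3.2.1.1). A 6-day hold on once-daily dosing leaves 21 − 6 = 15 doses, and 15/21 = 71.4%. That is below 75% and short of the 7-day criterion, so the subject is neither a DLT nor evaluable. For BID under the 75% rule, 11 to 13 missed doses do the same (31 to 29 of 42, 73.8% to 69.0%).

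**5. What one excluded subject does to the report.** Assume 1 DLT among 6 evaluable subjects and one further subject excluded as in step 4. Intervals are exact 95%, the convention in Protocol 8.4.

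| Handling of the excluded subject | DLT incidence | 95% CI |
|---|---|---|
| Excluded, as planned | 1/6 = 16.7% | 0.4 to 64.1 |
| Retained, not a DLT | 1/7 = 14.3% | 0.4 to 57.9 |
| Retained, counted as dose-limiting (outer bound) | 2/7 = 28.6% | 3.7 to 71.0 |

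The last row goes beyond the protocol's DLT definition and only marks the edge of the range.

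**The case against.** **The analysis set already settles who counts.** This stands. A reader might infer from 4.1.2 that a replaced subject's DLT drops out and that a dose level could clear because of it. The documents do not support that. Both DLT-Evaluable definitions keep any subject with a DLT in the window, and 4.1.2 says when another subject is enrolled, not who leaves an analysis. What remains is the extra subject, and the missing rule for 4 or 7.

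**Excluded subjects can be traced.** This also stands. A reader might infer that nobody could tell who was left out. SAP 4.1 tabulates the DLT-Evaluable and Safety sets by cohort. SAP 4.2.2 summarises adherence below and at or above 75% in the window, and lists dosing dates and interruption reasons by subject. The gap is narrower: the DLT table itself does not show these exclusions.

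**The BID problem is one of wording.** Largely true. The fraction 16/21 carries its own denominator, and it works for BID as a proportion or as dosing days. But both documents say doses, and neither says which reading is meant.

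**The toxicity-shortfall group is small, and a minimum-exposure condition is a legitimate choice.** Both parts are fair. Most Grade 3 or higher non-hematologic events, treatment-ending toxicity and longer holds are already DLTs. The discussion of laboratory events allowed by 3.2.1.1 may capture others. Escalation review also covers other adverse events (Protocol 8.2.1.1), and the RP2D draws on all treated subjects.

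**Conclusion.** The inconsistency is real and of moderate consequence. Followed as written, 4.1.2 replaces a once-daily subject whom the MTD set still counts, which produces cohort sizes of 4 or 7 without a decision rule. A literal count of 16 also classifies BID subjects with 16 to 31 of 42 doses differently from the 75% rule. The first conclusion assumes that the subject stays on study; the second assumes that doses means doses taken, not dosing days or a proportion.

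The loss of sub-DLT toxicity shortfalls from the denominator is a secondary point. The documents give no shortfall rate, so neither the size nor the direction of any effect on escalation can be determined. The 1/6, 1/7 and 2/7 figures are illustrations.

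SAP 1 says that the study was terminated during Phase 1b for lack of efficacy and that Phase 2 was not initiated. What is left is the reported DLT incidence and the MTD statement in a synoptic report.

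**What to change.** 1. Reconcile the synopsis, Protocol 3.2.1, 4.1.2 and 8.3.1.4, and SAP 1.2.1 and 3.1.4, so that the dose limb of the replacement rule agrees with the DLT-Evaluable definition for subjects with a DLT. Say what replaced means for the count.
2. State the documents' own 75% threshold as a share of prescribed doses for each regimen: 16 of 21 for QD and 32 of 42 for BID.
3. Optionally, footnote in the SAP 7.1.7 DLT table the number excluded for a toxicity-related dose shortfall, with one sensitivity row that retains them.

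How such shortfalls are adjudicated clinically is for the sponsor and the safety review team; no rule is proposed here.

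The cost is one clause, one threshold per regimen, and at most a footnote and a table row. The by-subject listing in SAP 4.2.2 already holds the dosing dates and interruption reasons. SAP 1 provides for changes after finalisation to be documented in the study report. One downside: retained subjects count as DLT-free on reduced exposure, so they belong in a sensitivity row and not in the main count.
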